6.2 Clinical Condition/Indication

The EU RPP is indicated for the treatment of moderate to severe chronic plaque psoriasis in adult patients who failed to respond to or who have a contraindication to, or are intolerant to other systemic therapy including cyclosporine, methotrexate (MTX), or phototherapy (psoralens and long-wave ultraviolet radiation [PUVA]).⁴

The medical need for a biosimilar to the EU RPP (adalimumab) is demonstrated with the approval and use of the originator product Humira and its place in the treatment of several chronic autoimmune or inflammatory diseases, including rheumatoid arthritis, juvenile idiopathic arthritis, psoriatic arthritis, ankylosing spondylitis, Crohn's disease, ulcerative colitis, and plaque psoriasis.

Provided that comparability of M923 to the EU RPP is demonstrated in all aspects of safety and efficacy, then the medical need for this product is also established.

6.3 Population to Be Studied

The study population will include 516 subjects with moderate to severe chronic plaque-type psoriasis. Adult (≥ 18 years) male and female subjects will be considered to be eligible provided that they satisfy all of the inclusion criteria listed in [Section 9.1](#) and none of the exclusion criteria listed in [Section 9.2](#).

6.4 Findings from Nonclinical and Clinical Studies

Multiple lots of the US RP and EU RPP have been extensively characterized in nonclinical pharmacology, PK, and immunogenicity studies and compared with the investigational M923 proposed adalimumab biosimilar product. The results of these comparisons showed that the biological activities of M923 corresponded to the comparators (both US RP and EU RPP). Specifically, the results were within the acceptance range for M923, EU RPP, and US RP for binding to soluble human TNF- α , the human Fc γ receptor, C1q complex, and the human neonatal Fc receptor; activity in the antibody-dependent cell-mediated cytotoxicity (ADCC) and complement-dependent cytotoxicity (CDC) assays; potency in the L929 mouse fibroblast cell line assay; PK and in vitro immunogenicity. A Phase 1 PK study with M923 in healthy volunteers is currently ongoing.

6.5 Evaluation of Anticipated Risks and Benefits of the Investigational Product(s) to Human Subjects

All risks, contraindications, precautions, dosage and administration considerations, drug interactions and overdosage considerations that have been described for Humira (both the EU RPP and the US RP) apply to M923 (see Appendix A of the Investigator's Brochure [IB] for M923). However, investigators should carefully monitor for all AEs, including AEs not described as associated with the EU RPP and the US RP.

6.6 Compliance Statement

This study will be conducted in accordance with this protocol, the International Council on Harmonisation Guideline for Good Clinical Practice E6 (ICH GCP, April 1996), Title 21 of the US Code of Federal Regulations, the EU Directives 2001/20/EC and 2005/28/EC, and the Declaration of Helsinki and applicable national and local regulatory requirements.

7. STUDY PURPOSE AND OBJECTIVES

7.1 Study Purpose

The purpose of the study is to evaluate efficacy, safety, and immunogenicity of M923 (a proposed adalimumab biosimilar) and a non-US-approved comparator (EU-approved Humira[®]) referred to as the Reference Protein Product (EU RPP) in subjects with moderate to severe chronic plaque-type psoriasis.

7.2 Primary Objective

The primary objective of the study is to demonstrate equivalence in measures of efficacy between M923 (test) and EU RPP (reference) in subjects with moderate to severe chronic plaque-type psoriasis.

7.3 Secondary Objectives

The secondary objectives of the study are to:

1. Evaluate the continued efficacy, safety, immunogenicity, and tolerability of M923 compared with EU RPP
2. Evaluate the transition from EU RPP to M923 based on safety and immunogenicity compared with continuous use of EU RPP
3. Evaluate concentrations over time

8. STUDY DESIGN

8.1 Brief Summary

This study is a Phase 3, active-controlled, randomized, double-blind, multicenter study to determine the clinical equivalence of M923 and EU RPP in a total of 516 randomized subjects (258 subjects in the M923 group and up to 129 subjects in each of 2 EU RPP crossover groups) with moderate to severe chronic plaque-type psoriasis.

8.2 Study Design

The 2 treatment arms will include:

- Arm A: M923 from Weeks 0 to 48 (last dose at Week 47)
- Arm B: EU RPP from Weeks 0 to 16 (last dose at Week 15); then randomized again at Week 16 into Arms B1 and B2:
 - Arm B1: Continues EU RPP from Weeks 17 through 48 (last dose at Week 47; n = up to 129 subjects)
 - Arm B2: Transition to M923 at Week 17; then to EU RPP at Week 25; and to M923 at Week 37 (last dose at Week 47; n = up to 129 subjects)

Subjects who complete the treatment period will have a safety follow-up visit at Week 52.

The overall study design is illustrated in [Figure 1](#).

8.3 Duration of Study Period(s) and Subject Participation

The overall duration of the study is 86 weeks from study initiation (ie, first subject enrolled) to study completion (ie, last subject last visit) The recruitment period was expected to be 8 months (actual duration was 7 months).

The subject participation period is approximately 56 weeks (4-week screening period, 48-week treatment period, and 4-week follow-up period) from enrollment to subject completion (ie, last study visit), unless prematurely discontinued.

8.4 Outcome Measures

8.4.1 Primary Outcome Measure

The primary outcome measure is the Psoriasis Area and Severity Index 75% improvement (PASI75) response rate at Week 16 in subjects treated with M923 vs EU RPP.

8.4.2 Secondary Outcome Measures

8.4.2.1 Efficacy

1. Proportion of subjects with response by static Physician Global Assessment (sPGA) of clear or almost clear (6-point scale) at Week 16 in subjects treated with M923 vs EU RPP
2. PASI50, PASI75, PASI90, and sPGA response rates over time in subjects treated with M923 or EU RPP
3. Absolute PASI score over time in subjects treated with M923 and EU RPP
4. Health-related quality of life during treatment with M923 and EU RPP based on the Dermatology Life Quality Index (DLQI) and the EuroQoL 5-Dimension Health Status Questionnaire (EQ-5D-5L)

8.4.2.2 Safety

1. Clinical safety and tolerability of M923 compared with EU RPP as assessed by vital signs, clinical laboratory results, electrocardiograms (ECGs), and AEs (including serious AEs [SAEs], withdrawal from the study because of an AE, discontinuation of study-specific therapy because of an AE, and injection site reactions)
2. Clinical safety and tolerability of the transitions between EU RPP and M923 (occurring twice in arm B2) compared with continuous use of EU RPP (arm B1) – See [Figure 1](#).

8.4.2.3 Pharmacokinetics and Immunogenicity

1. Exposure to M923 and EU RPP assessed as serum levels collected periodically throughout the treatment period
2. Immunogenicity of M923 and EU RPP assessed as proportion experiencing seroconversion, titer of anti-drug antibody (ADA) levels over time, and neutralizing ADA

3. Immunogenicity, as evidenced by the presence of ADAs, following the transition from EU RPP to M923 compared with continuous use of EU RPP assessed as proportion of subjects experiencing seroconversion; titer of ADA levels over time; and neutralizing ADA over time

8.5 Randomization and Blinding

This is a randomized, double-blind, active treatment clinical study. In order to minimize/avoid bias, subjects will be randomly assigned at the beginning of the study to 1 of 2 treatment regimens (M923 or EU RPP) at a ratio of 1:1, stratified by region (North America, Western Europe, and Eastern Europe/Asia).

At Week 16, subjects who were randomly assigned to EU RPP at the screening visit will be randomly assigned again into 1 of 2 treatment regimens (continue EU RPP from Weeks 17 through 48; or transition between M923 and EU RPP approximately every 12 weeks from Weeks 17 to 48) at a ratio of 1:1. Stratification will ensure balance of treatment assignment within region. The blocking scheme will be specified in the randomization specifications. Randomization will occur via an Interactive Response Technology (IRT) System until the targeted number of subjects in each treatment arm is achieved.

The investigational product (IP) blind shall not be broken by the investigator unless information concerning the IP is necessary for the medical treatment of the subject. In the event of a medical emergency, if possible, the medical monitor should be contacted before the IP blind is broken to discuss the need for unblinding.

For unblinding a subject's data, the investigator can obtain the treatment assignment by utilizing the IRT System.

An administrative interim database lock will occur at Week 25 to perform the primary analysis, as well as safety, PK and immunogenicity analysis over this time interval. The interim analysis will be executed by an unblinded team distinct from the study team. The study team will remain blinded, as appropriate, until final database lock.

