13.4.4.3 Pharmacokinetics and Immunogenicity

The methods of analysis for the secondary PK outcome measures (see [Section 8.4.2.3](#)) will be done on the PK population.

The serum levels will be summarized by treatment arm at each scheduled collection. In addition to descriptive statistics described in [Section 13.4](#), the geometric mean, corresponding 95% confidence interval, and the geometric coefficient of variation (CV) will also be presented. To evaluate whether of anti-adalimumab antibody formation will affect exposure, the summaries will be further stratified by ADA formation (subjects who did not form antibodies, subjects who formed ADAs, versus subjects who formed neutralizing ADAs). The within-subject variability (CV) in trough concentrations over time (from Week 17 to Week 41) will be determined for each subject, which will then be compared between treatment arms using an analysis of variance model with treatment as a fixed effect.

The transition from EU RPP to M923 as compared with continuous use of EU RPP with regard to PK will be evaluated using the descriptive statistics at each schedule time point and statistical comparison of within-subject variability.

Pharmacokinetic data from the study may also be used for population PK/pharmacodynamic analyses. If done, a separate analysis plan will be prepared and results will be reported separately from the Clinical Study Report. Population PK/PD analyses are not planned following the administrative interim database lock at Week 25.

The immunogenicity analysis will be done on the safety population.

Immunogenicity data (overall ADA results and titers, and neutralizing ADA results and isotype of ADA where applicable, and time to seroconversion) will be listed. A summary of the number and percent of subjects testing positive for ADA or neutralizing antibodies before the dose of M923 or EU RPP and at scheduled postdose assessments will be presented by treatment arm. The time to seroconversion will be summarized by treatment arm using mean, median, standard deviation and range where appropriate.

The number and percentage of subjects who had at least one ADA-positive result will be provided by treatment arm. Similar analysis may be done for subjects with predose ADA-negative results and with at least one postdose ADA-positive results as appropriate.

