5. STATISTICAL CONSIDERATIONS

In general, all efficacy, safety, PK, and immunogenicity variables will be summarized using descriptive statistics. Continuous variables will be summarized by sample size [n], mean, standard deviation [SD], median, minimum and maximum. Categorical variables will be summarized in frequency tables (n, frequencies, and percentages). Additional statistics will be provided for PK and immunogenicity data as described in [Section 9](#).

Individual subject data will be presented in listings.

In summary tables, minimum and maximum should have the same number of decimals as the original data; means, medians to have one more, SDs should have two more decimal. Percentages, including percentage changes, will be shown to 1 decimal place.

The equivalence testing of the primary outcome measure will use 90% confidence intervals for FDA submission and 95% confidence intervals for EMA submission. Formal hypothesis testing will be performed only for the equivalence testing of the primary outcome measure. For the other outcome measures, the treatment difference and both 90% and 95% confidence intervals for treatment differences will be displayed.

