7.2 Analysis of Secondary Efficacy Outcome Measure

The analysis of the secondary efficacy outcome measures (see [Section 3.1.2](#)) will be performed on the PP population and repeated on the mITT population.

Secondary efficacy outcome measures include PASI50, PASI90, and sPGA response rate at Week 16 (Visit 7). A PASI50 (or PASI90) responder at Week 16 is defined a subject who achieves at least 50% (or 90%) improvement in PASI score from baseline at Week 16. The sPGA response rate will be described as the proportion of subjects who have achieved a clear or almost clear response (sPGA score of 0 or 1) at Week 16

At Week 16, the treatment arms (Arm A and B) will be compared using PASI50, PASI90, and sPGA response rates. For response rates in each individual treatment arm, 95% confidence intervals will be calculated using the Clopper-Pearson method. Treatment differences and corresponding 90% and 95% confidence intervals in response rates between M923 and EU RPP will be calculated using the Newcombe score method and stratified by geographic region (North America, Western Europe, and Eastern Europe/Asia). The NRI method (see [Section 5.2](#)) will be used to handle missing data.

Descriptive statistics and 95% confidence intervals for the mean of PASI total score and percentage change from baseline will be provided by treatment arm and analysis period (Arm A and B up to Week 16; Arm A, B1, and B2 after Week 16) for each scheduled time point. No imputation for missing data will be applied (observed case).

PASI50, PASI75, PASI90, and sPGA response rate and 95% confidence intervals calculated using the Clopper-Pearson method will be summarized by treatment arm and analysis period (Arm A and B up to Week 16; Arm A, B1, and B2 after Week 16) for each scheduled time point.

Figures will be created to display the response rates and mean percentage change in PASI score over time and by treatment arm and analysis period (Arm A and B up to Week 16; Arm A, B1 and B2 after Week 16).

Health-related quality of life measures, DLQI and the EQ-5D-5L, will be summarized by treatment arm and analysis period (Arm A and B up to Week 16; Arm A, B1 and B2 after Week 16) and scheduled time point.

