9. EVALUATION OF PHARMACOKINETICS

Secondary PK outcome measures will be analyzed using the PK Analysis set.

For the interim analysis, this will include adalimumab concentration and immunogenicity data through Visit 11, Week 25 and will reflect 5 post-dose assessments on Weeks 8, 16, 17, 21 and 25.

Adalimumab serum levels will be summarized by treatment arm at each scheduled collection. In addition to the usual descriptive statistics, the geometric mean, corresponding 95% confidence interval (CI), and geometric coefficient of variation (CV) will also be presented. Concentrations that are below the limit of quantitation (BLQ) will be replaced with the lower limit of quantitation (LLOQ) for the computation of descriptive statistics. Missing concentrations will be treated as missing. Individual and geometric mean (95% CI) adalimumab concentrations will be graphically presented by treatment (A vs B through Week 16 and versus B1 and B2 following re-randomization).

To evaluate whether anti-adalimumab antibody formation will affect exposure, the summaries will be further stratified by ADA formation (subjects who did not form antibodies, subjects who formed ADAs, subjects who did not form neutralizing ADAs, versus subjects who formed neutralizing ADAs), as appropriate.

Figures will be also be generated to display arithmetic mean adalimumab concentrations versus study week grouped by treatment. Scatterplots and boxplots will also present

adalimumab concentrations stratified by ADA status and to explore the relationship between trough concentrations and ADA titres.

The within-subject variability (geometric CV) in trough concentrations (2 weeks postdose samples) over time (Week 17 to Week 41) will be determined for each subject, which will then be listed, summarized, and compared between treatment arms (EU RPP/EU RPP versus EU RPP/M923) using an analysis of variance model with treatment as a fixed effect. For the subgroup in the EU RPP treatment which is randomized to transition to M923 and back, the troughs

- collected in Weeks 21 and 25 fall into the first transition to M923,
- collected in Weeks 29 and 37 fall into the transition back to EU RPP,
- collected in Week 41 falls into the second transition to M923.

The transition from EU RPP to M923 as compared with continuous use of EU RPP with regard to PK will be evaluated using the descriptive statistics at each schedule time point and statistical comparison of within-subject variability.

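### The B1 v B2 comparison of within-subject trough variability leaves out region, although the Week 16 re-randomisation appears to be balanced by region: a small, nearly free improvement to one secondary PK analysis

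*Protocol*

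**What the plan says.** Protocol 8.5 sets the first randomisation to M923 or EU RPP "at a ratio of 1:1, stratified by region (North America, Western Europe, and Eastern Europe/Asia"). It then describes the second randomisation, of Arm B at Week 16, giving the 1:1 ratio but no stratum. The sentence straight after that, in the same paragraph, is "Stratification will ensure balance of treatment assignment within region". SAP 2.3 has the same sentence, at the start of the paragraph that follows its account of both randomisations. Both documents leave the blocking scheme to separate randomisation specifications.

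The planned size of the re-randomised arms is in Protocol 8.2, for example "Arm B1: Continues EU RPP from Weeks 17 through 48 (last dose at Week 47; n = up to 129 subjects").

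One model compares these arms. SAP 9 takes each subject's geometric CV of trough concentrations over Weeks 17 to 41, to be "compared between treatment arms (EU RPP/EU RPP versus EU RPP/M923) using an analysis of variance model with treatment as a fixed effect". Protocol 13.4.4.3 has the matching text: "compared between treatment arms using an analysis of variance model with treatment as a fixed effect". Neither adds region.

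Region is used elsewhere. SAP 7.1.1 and 7.2 stratify the Newcombe intervals for M923 v EU RPP at Week 16 by region, and the MMRM in SAP 5.2 includes it as a covariate.

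**The concern.** When allocation is balanced within strata, differences between strata cannot contribute to the difference between arms, so the true sampling error of the treatment difference is smaller than under simple randomisation. A model without the strata does not know this. It leaves the between-region variance in the residual, and the standard error it reports is larger than the design warrants.

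At stake is the reported precision of a single secondary PK comparison. The direction matters a little. Both documents rely on this comparison in evaluating the PK of the transition, and there an overstated standard error makes a real difference in variability easier to miss.

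**Working it through.** The documents state no standard error, SD, effect size or power for this comparison, so there is no figure of the plan's own to reproduce. The arm size does check: 258/2 = 129.

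**Inputs**
- n = 129 per arm (Protocol 8.2, planned maximum).
- Three regions: North America, Western Europe, Eastern Europe/Asia (Protocol 8.5, SAP 2.3).
- Two-sided 5% level (default in Protocol 13.4), used here only to express the effect on coverage and rejection rate.
- R2, the share of variance in the subject-level CV explained by region: not in the documents. Assumed to be 2%, 5% or 10%.
- Outcome SD set to 1; it cancels from the ratio.
- Allocation balanced within region at Week 16: inferred, as set out above.

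**Formulas**
- Variance reported by the treatment-only ANOVA: 2·SD²/n.
- True variance under balanced allocation: (1-R2)·2·SD²/n.
- Reported SE / true SE = 1/sqrt(1-R2).
- Actual rejection rate at nominal 5%: P(|Z| > 1.96/sqrt(1-R2)).
- Power of the treatment-only test for an effect that the region-adjusted model detects with 80% power: Φ(2.8016 - 1.96/sqrt(1-R2)), where 2.8016 = 1.96 + 0.8416.

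**Results**

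The SE without region is sqrt(2/129) = 0.1245 in every row.

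| Assumed R2 | SE with region | SE too large by | Actual rejection rate | Coverage of 95% interval | Power instead of 80% |
|---|---|---|---|---|---|
| 2% | 0.1233 | 1.0% | 4.8% | 95.2% | 79.4% |
| 5% | 0.1214 | 2.6% | 4.4% | 95.6% | 78.5% |
| 10% | 0.1181 | 5.4% | 3.9% | 96.1% | 76.9% |

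**Break-even.** Adding region spends 2 of 258 - 2 = 256 residual degrees of freedom. The residual mean square falls only if (1-R2)/254 < 1/256, that is, if R2 > 2/256 = 0.0078, or about 0.8%.

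**Simulation.** This used 8,000 trials per setting with 129 per arm, and regions split 20/20/60 or in equal thirds (both assumed). At R2 = 10% with balanced allocation, the ratio of reported to true SE was 1.060 and 1.046, and the rejection rate under no difference was 3.9% and 3.8%. With region in the model the rejection rate was 5.0% and 4.8%. At 2% and 5% the simulated ratios (1.000 to 1.018) were slightly below the formula. The simulation error of the ratio is about 1/sqrt(2 × 8000) = 0.008, so they do not contradict it. Without stratified allocation, at R2 = 20%, the ratio was 0.99 and the rejection rate 5.2%. The overstatement therefore comes from stratifying and then omitting the stratum, not from omitting region as such.

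**Sample size.** Protocol 13.5 puts 572 subjects in the final analysis, so the arms could reach about 572/4 = 143. Subjects lost after Week 16 reduce the number analysed. The ratio does not depend on n. Uneven losses across regions would loosen the balance, so 1/sqrt(1-R2) is the full-balance figure.

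**The case against.** Four objections have force.

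1. **Week 16 stratification is not stated outright.** The words that name the strata belong to the first randomisation. The re-randomisation text, the notes under the study schematic and the footnote to the schedule of assessments name no stratum. This stands. Position makes the balance sentence most naturally cover both randomisations, but that is an inference. If it is wrong, the treatment-only SE is valid.

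2. **The effect is small and R2 has no source.** This stands. The outcome also argues for the lower end of the range: a regional factor that scales all of a subject's troughs equally cancels out of that subject's CV.

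3. **Nothing formal hangs on the comparison.** SAP 5 confines formal hypothesis testing to the primary outcome. This stands, and it limits the point to the accuracy of a reported standard error.

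4. **The point must not be stretched to the switching objective.** A reader might infer that the intervals for safety and immunogenicity after switching are too wide as well. The documents do not support that. The second secondary objective concerns safety and immunogenicity, and Protocol 13.4.4.2 and 13.4.4.3 and SAP 8.1 and 10 evaluate the transition on these with counts, percentages and summary statistics, which have no standard error to inflate. SAP 5 does say for other outcomes that "the treatment difference and both 90% and 95% confidence intervals for treatment differences will be displayed", but it names neither B1 v B2 nor anti-drug antibodies and gives no interval method for them.

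Nor does the calculation above support region-stratified Newcombe intervals for antibody rates, because it is for a linear model. In a simulation with an assumed 10% rate in every region and 26, 26 and 77 subjects per arm by region, a stratified Newcombe interval came out slightly wider than the unstratified one (mean width 0.154 v 0.151).

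**Conclusion.** The point holds as an optional improvement to one secondary PK analysis. If the Week 16 re-randomisation is balanced within region, the treatment-only ANOVA of within-subject trough CV reports a standard error that is too large: by 1.0% to 5.4% for an assumed R2 of 2% to 10%, and with nothing to gain below about 0.8%. The error is conservative for declaring a difference and mildly unhelpful for detecting one. If Week 16 was not stratified, the analysis is valid as written and a region term would only add precision when region predicts the outcome.

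A reader might infer that the omission weakens the equivalence claim. It does not: the primary analysis compares Arms A and B at Week 16, and SAP 7.1.1 already stratifies it by region.

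**What to change.** - In SAP 9, and for consistency Protocol 13.4.4.3, add randomisation region (North America, Western Europe, Eastern Europe/Asia) as a fixed effect alongside treatment in the ANOVA of within-subject trough CV.
- In SAP 2.3, state outright that the Week 16 re-randomisation is stratified by region, after checking this against the randomisation specifications. If it was not stratified, say so; the region term then becomes a choice made for precision alone.

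The cost is one model term, two residual degrees of freedom out of about 256, and a line of text. No data collection, sample size or primary analysis changes. Nothing needs to change in the safety or immunogenicity summaries on this account.
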